6.3. Adjustments for Covariates

No statistical tests will be performed.

6.4. Handling of Dropouts or Missing Data

Depending on the estimand being addressed, different methods will be used to handle missing data. A description of the estimands can be found in Section 6.2.

For the primary objective, no supportive estimand or sensitivity analysis will be performed.

For the primary estimand of the secondary objective, missing data, including data missing as a result of ICEs, will be imputed based on Markov Chain Monte Carlo – Multiple imputations (MCMC-MI) as described in Section 6.4.3. An as observed analysis (see Section 6.4.1) and last observation carried forward (LOCF) (see Section 6.4.2) will be used in the supportive estimands of secondary objective.

Table KGAA.6.3 describes the planned imputation methods for efficacy and health outcome endpoints for the treatment period.

Table KGAA.6.3. Imputation Techniques for Various Variables During Treatment Period

Type of Endpoints	Efficacy and Health Outcome Endpoints	Estimand of Secondary Endpoints (Analysis Strategy for Intercurrent Events)	Missing Data Imputation Method
Categorical	IGA, EASI, Pruritus NRS, Skin Pain NRS, and Sleep-loss related categorical	Primary Estimand	MCMC-MI/As Observed ^b
	endpoints at pre-specified timepoints ^a	Supportive Estimand	As Observed, LOCF
	Remaining categorical endpoints	Supportive Estimand	As Observed, LOCF
Continuous	EASI percent change, Pruritus NRS percent change, Skin Pain NRS percent	Primary Estimand	MCMC-MI/As Observed ^b
	change, and Sleep-loss change from Baseline ^a	Supportive Estimand	As Observed, LOCF
	Remaining continuous endpoints were collected at multiple postbaseline timepoints including (but not limited to) BSA, and POEM	Supportive Estimand	As Observed, LOCF

Abbreviations: BSA = body surface area; EASI = Eczema Area and Severity Index; IGA = Investigator's Global Assessment; LOCF = last observation carried forward; MCMC-MI = Markov chain Monte Carlo multiple imputation; NRS = Numeric Rating Scale; POEM = Patient-Oriented Eczema Measure.

- ^a Pruritus NRS, Skin Pain NRS, Sleep-loss is assessed only up to week 52. Skin Pain NRS is only collected for patients enrolled from KGAK. Pruritus NRS and Sleep-loss are not collected for patients enrolled from KGAE.
- b MCMC-MI will be implemented for the following two analysis groups only: 1. Patients coming from parent study KGAD (DRM06-AD06) who were lebrikizumab Q2W responders in KGAD and then were randomized in KGAA, by treatment group in KGAA; 2. Patients coming from parent studies KGAB (DRM06-AD04) and KGAC (DRM06-AD05), received lebrikizumab 250 mg Q2W during parent study induction period and received lebrikizumab 250 mg Q2W or lebrikizumab 250 mg Q4W during the maintenance period and not in escape arm. For other analysis groups, As Observed will be missing data imputation method.

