6.4.3. Markov chain Monte Carlo-Multiple Imputation

This method of imputing missing data will be used to implement the primary estimand of the secondary objective. This method will only be implemented for the following two analysis groups:

- 1. Patients coming from parent Study KGAD (DRM06-AD06) who were lebrikizumab Q2W responders in KGAD and then were randomized in KGAA, by treatment group in KGAA.
- Patients coming from parent Studies KGAB (DRM06-AD04) and KGAC (DRM06-AD05), received lebrikizumab 250 mg Q2W during the parent study induction period and received lebrikizumab 250 mg Q2W or lebrikizumab 250 mg Q4W during the maintenance period and are not in the escape arm.

For patients who discontinue from the study treatment due to lack of efficacy, set the patient's baseline value subsequent to this time through Week 100. The MCMC-MI will be used to handle the remaining missing data. Imputation will be conducted within each treatment group and for different parent studies (including Protocol KGAA Addendum 1.1) independently so the pattern of missing observations in 1 imputation group cannot influence missing value imputation in another. For each imputation process, 25 datasets with imputations will be calculated. The initial seed values are given in Table KGAA.6.4. The SAS PROC MI with MCMC option will be used to conduct the MCMC-MI. Each complete data set will be analyzed with the specified analysis. The results from these analyses will be combined into a single inference using SAS PROC MIANALYZE.

For binary responses related to EASI and IGA, the binary response variables will be calculated based on the multiply imputed datasets that have been created. As the MCMC algorithm is based on the multivariate normal model, imputed values for IGA will not generally be one of the discrete values used in IGA scoring (0, 1, 2, 3, or 4). Therefore, to derive the binary IGA response variable, standard rounding rules will be applied to the imputed values. For example, if a patient has an IGA score imputed as 1.4 (and assuming a baseline IGA score of 3), the imputed value would be rounded down to 1, and the minimum change from a baseline of 2 would have been met. This patient would be considered a responder.

For derivation of an EASI-75 and EASI-90 response, no rounding will be performed. The imputed EASI value will be compared directly to the observed Baseline EASI value to determine whether a reduction of at least 75% or 90% was achieved.

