The approach to handling missing data for Pruritus NRS, Skin Pain NRS, and Sleep-loss are the same. We use Pruritus NRS as an example. For derivation of the following Pruritus NRS responses, no rounding will be performed. The imputed Pruritus NRS value will be compared directly to the observed mean baseline Pruritus-NRS value to determine whether a response was achieved:

Percentage of patients with a Pruritus NRS of \geq 4-points at Baseline who achieve a \geq 4-point reduction from Baseline.

Imputation of continuous data will parallel that of binary variables. The imputed values will be used for the secondary endpoints such as:

- Percentage change in Pruritus NRS score from Baseline to Week 52 (for studies in which these data were collected).
- Percentage change in EASI score from Baseline at each visit.

Table KGAA.6.4. Seed Values for MCMC-Multiple Imputation

Analysis	Seed values
IGA and its related derived endpoints.	724145708
EASI and its related derived endpoints.	175356158
Pruritus NRS and its related derived endpoints.	1339532552
Sleep-lose due to pruritus and its related derived endpoints.	234325234
Skin Pain NRS and its related derived endpoints.	454236342

Abbreviations: EASI = Eczema Area and Severity Index score; IGA = Investigator's Global Assessment for AD; MCMC = Markov Chain Monte Carlo; NRS = Numeric Rating Scale.

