	3-4 days = 2; $5-6 days = 3$; everyday	Change from baseline	Change from baseline: observed POEM	Missing if baseline or
	= 4). A high score is indicative of a	in POEM score	score – baseline POEM score	observed value is
	poor quality of life. POEM responses			missing.
	will be captured using an electronic	4-point improvement	Change from baseline ≤-4	Missing if baseline is
	diary and transferred into the clinical	_		missing or observed
	database.			value is missing.

Abbreviations: AD = atopic dermatitis; BAS = Body Surface Area; EASI = Eczema Area and Severity Index; IGA = Investigator's Global Assessment; N/A = not applicable; NRS = Numeric Rating Scale; POEM = Patient Oriented Eczema Measure; TCI = Topical Calcineurin Inhibitors; TCS = Topical corticosteroids.

- a Secondary endpoints.
- b Daily pruritus, sleep-loss, and weekly/in-office POEM were only collected for patients participating in Studies KGAB, KGAC, KGAD, and KGAK.
- c TCS/TCI data, only collected for patients participating in Study KGAD.
- d Daily Skin-pain NRS only collected for patients participating in Study KGAK.

 Table KGAA.6.7.
 Description of Efficacy/Health Outcome Analyses

			Population		
Measure	Variable	Analysis Method	(Section 6.1.1)	Time Point	Analysis Type
IGA	Proportion of patients	Descriptive analysis	mITT	All scheduled visits in the	Secondary analysis
	achieving IGA (0,1)	with MCMC-MI ^a		Treatment Period at which scales	
				are collected	
	Proportion of patients	Descriptive analysis	mITT	All scheduled visits in the	Supplementary analysis
	achieving IGA (0)	with As Observed		Treatment Period at which scales	
				are collected	
		Descriptive analysis	mITT	All scheduled visits in the	Supplementary analysis
		with LOCF		Treatment Period at which scales	
				are collected	
EASI	Change from baseline in EASI	Descriptive analysis	mITT	All scheduled visits in the	Secondary analysis
	score	with MCMC-MI ^a		Treatment Period at which scales	
				are collected	
	Percent change from baseline	Descriptive analysis	mITT	All scheduled visits in the	Supplementary analysis
	in EASI score	with As Observed		Treatment Period at which scales	
				are collected	
		Descriptive analysis	mITT	All scheduled visits in the	Supplementary analysis
		with LOCF		Treatment Period at which scales	
				are collected	
	Proportion of patients	Descriptive analysis	mITT	All scheduled visits in the	Secondary analysis
	achieving EASI-75	with MCMC-MI ^a		Treatment Period at which scales	
				are collected	

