	Change from baseline in Sleep-loss Score Proportion of patients achieving at least 2-point improvement sleep-loss in	Descriptive analysis with As Observed	mITT	All scheduled visits in the Treatment Period at which scales are collected	Supplementary analysis
		Descriptive analysis with LOCF	mITT	All scheduled visits in the Treatment Period at which scales are collected	Supplementary analysis
		Descriptive analysis with MCMC-MI ^a	mITT patients with baseline Sleep-loss ≥ 2	All scheduled visits in the Treatment Period at which scales are collected	Secondary analysis
	patients who had baseline Sleep-loss ≥ 2	Descriptive analysis with As Observed	mITT patients with baseline Sleep-loss ≥ 2	All scheduled visits in the Treatment Period at which scales are collected	Supplementary analysis
		Descriptive analysis with LOCF	mITT patients with baseline Sleep-loss ≥ 2	All scheduled visits in the Treatment Period at which scales are collected	Supplementary analysis
Skin Pain NRS	Percent Change from baseline in Skin Pain Score	Descriptive analysis with MCMC-MI ^a	mITT	All scheduled visits in the Treatment Period at which scales are collected	Secondary analysis
	Change from baseline in Skin Pain Score	Descriptive analysis with As Observed	mITT	All scheduled visits in the Treatment Period at which scales are collected	Supplementary analysis
		Descriptive analysis with LOCF	mITT	All scheduled visits in the Treatment Period at which scales are collected	Supplementary analysis

Description of Efficacy/Health Outcome Analyses

			Population		
Measure	Variable	Analysis Method	(Section 6.1.1)	Time Point	Analysis Type
Skin Pain NRS	Proportion of patients	Descriptive analysis	mITT patients	All scheduled visits in the	Secondary analysis
	achieving at least a 4-point	with MCMC-MI ^a	with baseline	Treatment Period at which scales	
	improvement in Skin Pain		Skin Pain NRS	are collected	
	NRS in patients who had		≥4		
	baseline Skin Pain NRS ≥4	Descriptive analysis	mITT patients	All scheduled visits in the	Supplementary analysis
		with As Observed	with baseline	Treatment Period at which scales	
			Skin Pain NRS	are collected	
			≥4		
		Descriptive analysis	mITT patients	All scheduled visits in the	Supplementary analysis
		with LOCF	with baseline	Treatment Period at which scales	
			Skin Pain NRS	are collected	
			≥4		
POEM	Change from baseline in	Descriptive analysis	mITT	All scheduled visits in the	Secondary analysis
	POEM score	with As Observed		Treatment Period at which scales	

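### The secondary MCMC-MI analyses of Skin Pain NRS contain no patients, and no Skin Pain analysis that can be run applies the composite lack-of-efficacy rule

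*SAP*

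**What the plan says.** **Who has the data.** Footnote a of Table KGAA.6.3 in the SAP states that "Skin Pain NRS is only collected for patients enrolled from KGAK". Footnote d of Table KGAA.6.6 agrees: "Daily Skin-pain NRS only collected for patients participating in Study KGAK". The revision history in Section 3 gives the same restriction.

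**Who gets MCMC-MI.** Footnote b of Table KGAA.6.3 says "MCMC-MI will be implemented for the following two analysis groups only": KGAD lebrikizumab responders randomised in KGAA, and a subset of KGAB and KGAC patients defined by induction and maintenance treatment. Section 6.4.3 repeats it ("This method will only be implemented for the following two analysis groups"), as does footnote a of Table KGAA.6.7.

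**What is planned for Skin Pain.** Table KGAA.6.3 gives MCMC-MI or As Observed under the primary estimand. Section 6.4.3 treats Skin Pain like Pruritus NRS, and Table KGAA.6.4 assigns seed 454236342 to "Skin Pain NRS and its related derived endpoints". In Table KGAA.6.7, the block that begins "Percent Change from baseline in Skin Pain Score" and the 4-point response block each have MCMC-MI as the secondary analysis, with As Observed and LOCF as supplementary.

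**The estimand.** Section 6.2.2 applies the primary estimand to every secondary endpoint. Under Table KGAA.6.2, that means a return to baseline after a stop for lack of efficacy and MCMC-MI for other missing values. As Observed and LOCF are listed there as supportive.

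**The concern.** The patients who have Skin Pain data and the patients eligible for MCMC-MI come from different parent studies. If the two sets do not overlap, the analysis that the SAP ranks first for Skin Pain cannot be produced, and only analyses that it ranks lower remain.

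What is at stake is the question the reported figure answers. The primary estimand counts a patient who stops for lack of efficacy as a failure. Section 5.1.2 calls for patients who do not reach or keep EASI-50 to be terminated from the study, and Appendix 1 maps Skin Pain to visits up to Week 52. A summary of those still on treatment at the later visits therefore describes a group selected partly on response.

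**Working it through.** No sample size or power figure is involved. The check compares sets of patients, then compares how each method treats a stop for lack of efficacy.

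**1. Overlap**
- Parent studies with Skin Pain data: {KGAK} (Section 3; Table KGAA.6.3 footnote a; Table KGAA.6.6 footnote d).
- Parent studies eligible for MCMC-MI: {part of KGAD, part of KGAB/KGAC} (Table KGAA.6.3 footnote b; Section 6.4.3; Table KGAA.6.7 footnote a).
- Section 5.3 assigns treatment by each patient's own parent trial, so a patient has one parent study.
- Intersection: empty. Patients in the Skin Pain MCMC-MI analyses: 0.

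**2. Contrast.** Footnote b of Table KGAA.6.6 has Pruritus NRS and Sleep-loss collected in KGAB, KGAC, KGAD and KGAK. Their overlap with the MCMC-MI groups is not empty. The fault is specific to Skin Pain.

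**3. Table KGAA.6.7, Skin Pain entries.** Two blocks (change with percent change; 4-point response) times three methods make 6 entries.
- Secondary: 2 entries, both MCMC-MI, both with no patients.
- Supplementary: 4 entries (As Observed and LOCF in each block), all runnable.

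**4. A patient who stops for lack of efficacy, 4-point response**
- Primary estimand: value set to baseline, change 0, which does not meet the criterion of −4 or lower. Non-responder.
- As Observed (Section 6.4.1): not a completer at the visit, so not counted.
- LOCF (Section 6.4.2): later values set to missing and the last one carried forward. Responder or non-responder according to that last value.

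**5. Direction and size.** Let n patients be observed at a visit, R of them responders, and let L have stopped for lack of efficacy. For simplicity, assume no other missing data. Let k of the L stoppers have a last value that met the criterion (0 ≤ k ≤ L).
- As Observed = R / n
- Composite = R / (n + L) = (R / n) × (1 − s), where s = L / (n + L)
- LOCF = (R + k) / (n + L)

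The composite rate cannot exceed either of the other two. It equals As Observed only when s = 0 (or R = 0), and LOCF only when k = 0. The documents give none of n, R, L or k for KGAK, so no numerical difference can be computed.

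**The case against.** The best reply is that the plan is not silent. The primary-estimand cell in Table KGAA.6.3 names As Observed next to MCMC-MI, and footnote b sends every other group, hence KGAK, to As Observed. A reader might infer that Skin Pain has no planned analysis, or falls to As Observed by accident. The documents do not support that: the fallback is written down. It supplies a method, however, and not the estimand. Table KGAA.6.2 lists As Observed as a separate supportive estimand, and Section 6.4.1 itself says that it is conditional on staying on treatment and not causal. Table KGAA.6.7 also labels it supplementary, and footnote a of that table omits the fallback.

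A reader might also infer that patients who stop for lack of efficacy vanish from every Skin Pain result. They do not: LOCF keeps them in the denominator and can use parent-study observations. It still does not count them as failures.

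Nor does it matter here that KGAK appears in Section 6.1.3 only in combination with KGAD. KGAD patients have no Skin Pain data, so the as-observed summary of that group already contains KGAK patients alone.

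Finally, the stakes are modest. Skin Pain is among the other secondary endpoints, the analysis is descriptive and nothing is tested. The two-group limit also leaves KGAK on As Observed for IGA and EASI. That is fair, but those endpoints keep two groups in which the primary estimand is estimated. Skin Pain keeps none.

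**Conclusion.** The inconsistency is real. Both Skin Pain entries that Table KGAA.6.7 calls secondary, and the Skin Pain seed, apply to 0 patients. All four runnable entries are supplementary, and none applies the composite rule that Section 6.2.2 sets for all secondary endpoints. The primary estimand is therefore not estimated for Skin Pain in any group.

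The empty overlap rests on the SAP's own collection and scope statements, each given three times, and on one parent study per patient. The direction in step 5 also assumes no other missing data. It would be going too far to say that the reported results are biased by a given amount: the size depends on the KGAK discontinuation counts, which are not in the documents. This should be corrected because it is wrong as written and cheap to repair, but it does not bear on the study's primary endpoint or its major secondary endpoints.

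**What to change.** **Preferred.** State that, for Skin Pain NRS, the composite rule and MCMC-MI are run in KGAK patients. Make the change in all three places that carry the limit: the text of Section 6.4.3, footnote b of Table KGAA.6.3 and footnote a of Table KGAA.6.7. Changing only the footnotes would leave Section 6.4.3 contradicting them. Use the imputation cells already in Section 6.4.3 (treatment group within parent study) and seed 454236342. Section 5.3 gives all KGAK patients Q2W maintenance, so this is a single cell, and no split by former parent arm is needed. Label the run post hoc: the revision history shows that Version 3 records analyses from a clinical study report approved on 22 January 2025.

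The cost is three text edits and one imputation run of 25 datasets on data already collected. The drawback is that this one endpoint would be handled differently from the other KGAK endpoints, which stay on As Observed.

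**If the two-group limit is kept.** Remove the Skin Pain MCMC-MI entries from Table KGAA.6.7 and the seed from Table KGAA.6.4, with matching edits to Table KGAA.6.3 and Section 6.4.3. Name As Observed as the lead Skin Pain analysis. State that its result is conditional on remaining on treatment and does not estimate the composite estimand. This costs text only.

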6.2.2. Estimands of Secondary Objectives (Efficacy)

The secondary clinical question of interest is: what is the proportion of patients who meet the clinical requirements for response AND without discontinuation due to lack of efficacy?

The primary estimand of the secondary objective is described by the following attributes:

- A. Population: modified intent-to-treat (mITT) population as defined in Section 6.1.1;
- B. Variable: apply to all secondary endpoints.
- C. How to account for intercurrent events (ICEs):
 - a. Subjects who discontinued treatment due to lack of efficacy during Study KGAA will be considered as treatment failures, that is, nonresponders, after the ICEs. Therefore, a composite strategy will be used for these types of ICEs.
 - b. For subjects who discontinued treatment due to any other reasons, the hypothetical strategy will be used to estimate what the treatment effect would have been if subjects continued with treatment. Therefore, the hypothetical strategy will be used for these ICEs
- D. Population-level summary: response proportions or means.

The **first supportive estimand of the secondary objective** is described by the following attributes:

- A. Population: mITT population as defined in Section 6.1.1;
- B. Variable: apply to all secondary endpoints.
- C. How to account for ICEs: as observed strategy will be used, that is, only data from completers at the visit are relevant.
- D. Population-level summary: response proportions or means.

The **second supportive estimand of the secondary objective** is described by the following attributes:

- A. Population: modified ITT population as defined in Section 6.1.1;
- B. Variable: apply to all secondary endpoints.
- C. How to account for ICEs: for subjects who discontinue treatment, the hypothetical strategy will be used to estimate what the treatment effect would have been if all subjects adhered to the treatment. Therefore, the hypothetical strategy is used for these types of ICEs.
- D. Population-level summary: response proportions or means.

Analytical details on how missing data, including data missing as a result of intercurrent events, will be handled can be found in Section 6.4. Endpoints will be analyzed as described in Section 6.11 and Section 6.14. No statistical test will be performed.

Table KGAA.6.2. summarizes different analyses that will be conducted on the secondary endpoints.

Table KGAA.6.2. Analysis of Secondary Endpoints

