	Treatment Discontinuation		Missing Data Imputation	
Estimand	Due to lack of efficacy	Due to any other reasons	Missing Data Imputation Method	
Primary	Composite: Set to baseline	Hypothetical: Set to missing	MCMC-MI	
Supportive	As observed	As observed	As observed analysis	
Supportive	Hypothetical: Set to missing	Hypothetical: Set to missing	LOCF	

Abbreviations: LOCF = last observation carried forward; MCMC-MI = Markov Chain Monte Carlo – Multiple imputation.

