6.4.1. As Observed Analysis

The "as observed" strategy is used in the so-called "observed cases" or "completers" analysis ubiquitous in the literature, though is not one of the recommended strategies in the ICH E9(R1). For this analysis, only data from completers at the visit are relevant. This estimand is conditional and targets the effect of treatment conditional on completion of treatment through the timepoint of interest. As the estimand is defined for a subpopulation conditional on an ICE, it is not considered causal. A summary based on observed data at each postbaseline visit will be provided. All efficacy data will be summarized using an "as observed" analysis.

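### SAP Table KGAA.6.3 puts As Observed under the primary efficacy estimand for four of six analysis groups, and on neither possible reading does it estimate the quantity SAP 6.2.2 defines

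*SAP*

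**What the plan says.** SAP 6.2.2 sets a primary estimand for the secondary (efficacy) objective in the mITT population, with no limit by analysis group. "Subjects who discontinued treatment due to lack of efficacy during Study KGAA will be considered as treatment failures", a composite strategy; stops for other reasons get a hypothetical strategy. As Observed is defined separately, as the first supportive estimand.

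The primary row of Table KGAA.6.2 has "Composite: Set to baseline" for lack of efficacy and MCMC-MI as its only imputation method. The text of 6.4 agrees: for this estimand "missing data, including data missing as a result of ICEs, will be imputed based on Markov Chain Monte Carlo", while As Observed and LOCF "will be used in the supportive estimands of secondary objective".

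Table KGAA.6.3 then lists MCMC-MI and As Observed together in both Primary Estimand rows. Footnote b keeps MCMC-MI for two groups and says of the rest: "For other analysis groups, As Observed will be missing data imputation method". Section 6.4.3 has the same limit ("This method will only be implemented for the following two analysis groups"), as does footnote a of Table KGAA.6.7.

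On As Observed, 6.4.1 says: "For this analysis, only data from completers at the visit are relevant". It calls the result conditional on completing treatment and not causal. The operational step of assigning the "baseline value subsequent to this time through Week 100" after a lack-of-efficacy stop is in 6.4.3.

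**The concern.** The strategy for intercurrent events is part of the estimand. If the method changes by group under an unchanged label, the tables under that label may answer different questions. 6.2.2 asks for the proportion who respond and have not stopped for lack of efficacy. Poor responders are expected to leave: 5.1.2 directs termination of patients who do not reach or keep EASI-50 or who lack clinical benefit. How those exits are counted therefore affects IGA 0/1 and EASI-75, the major secondary endpoints.

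Consistency is also at stake. Two of the four As Observed groups contain the two MCMC-MI groups. If As Observed means completers only, the same lack-of-efficacy stop is a failure in the smaller table and absent from the larger one.

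**Working it through.** **1. Count and overlap.** SAP 6.1.3 lists six groups. MCMC-MI applies to two: KGAD Q2W responders randomised in KGAA, and KGAB/KGAC patients on Q2W induction then Q2W or Q4W maintenance, outside the escape arm. That leaves 6 − 2 = 4: KGAD+KGAK, KGAB+KGAC, KGAE and direct entry. The first two contain the MCMC-MI groups; KGAE and direct entry overlap with nothing. Patients in no MCMC-MI analysis are all of KGAE, KGAK and direct entry, plus the rest of KGAD and KGAB/KGAC (for example KGAD Week 16 non-responders, former placebo patients and escape-arm patients; see 5.3).

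**2. Two readings.**
- (a) As Observed means completers only, as 6.4.1 says. Lack-of-efficacy stops leave the denominator, and the row duplicates the first supportive estimand.
- (b) As Observed replaces only the imputation step. Tables KGAA.6.2 and 6.3 keep intercurrent-event strategy and imputation method in separate columns, and footnote b describes As Observed as an imputation method. Lack-of-efficacy stops then remain failures, and only other missing patients are left out.

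**3. Formulas.** At a given visit, L is the share stopped for lack of efficacy, D the share missing for other reasons, p the completer response rate and q the response rate the other dropouts would have had.
- 6.2.2 target: T = p(1 − L − D) + qD
- Reading (a): A = p
- Reading (b): B = p(1 − L − D)/(1 − D)

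**4. Inputs.** L, D and q are not in the documents. I assume L = 2%, 5% and 10%; other dropout of 30% among patients not stopped for lack of efficacy, so D = 0.30(1 − L); and q = p, so that T = p(1 − L). For scale only, p = 83%, the hypothesised Q4W EASI-75 rate in Protocol Addendum (11), 2.13, which concerns a different cohort.

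| L | T | A | A − T | B | B − T |
|---|---|---|---|---|---|
| 2% | 81.34% | 83.00% | +1.66 | 80.65% | −0.69 |
| 5% | 78.85% | 83.00% | +4.15 | 77.20% | −1.65 |
| 10% | 74.70% | 83.00% | +8.30 | 71.63% | −3.07 |

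Example for B at L = 10%: 0.83 × 0.90 × 0.70 / (0.90 × 0.70 + 0.10) = 0.5229/0.73 = 71.63%.

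With q = p, A − T = pL. At p = 69% (the hypothesised Q8W rate in the same section) this is 1.38, 3.45 and 6.90 points. The relative excess L/(1 − L) is 2.0%, 5.3% and 11.1% whatever p is.

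**5. When the signs change.**
- Reading (a): A − T = pL + (p − q)D, which is negative only if q/p − 1 > L/D. With p = 83%, L = 2%, D = 25% and q = 1.1p = 91.3%: 1.66 − 8.3 × 0.25 = −0.4 points.
- Reading (b): B − T = D(B − q), so B is too low only while q exceeds B. At L = 2%, D = 0.30 × 0.98 = 0.294; with q = 0.9p = 74.7%, B − T = 0.294 × (80.65 − 74.70) = +1.7 points.

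**6. Timing under (a).** A patient who fails at a visit still counts there and drops out afterwards, so the gap starts near zero. If stops accrued evenly after Week 16 to 10% at Week 100 (assumed), with p = 83%, the gap 0.83 × 0.10 × (w − 16)/84 is 0 at Week 16, 1.2 at Week 28, 3.6 at Week 52 and 8.3 points at Week 100.

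**The case against.** The two-group limit is deliberate. The revision history logs it as a clarification of MCMC-MI scope, it is repeated in 6.4.3 and Table KGAA.6.7, and 6.2.2 sends the reader to 6.4 for the handling of missing data. Table KGAA.6.7 already labels the As Observed and LOCF rows for IGA and EASI as supplementary, and 6.4.1 is candid about the limits of As Observed. Efficacy is secondary and descriptive, with no tests. LOCF is planned, and under it a patient terminated for failing EASI-50 stays an EASI-75 failure. Disposition is summarised with the reason for discontinuation (6.7), by the same groups (6.1.3).

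All of this stands and lowers the severity. It does not remove the conflict: the limit was never carried back into 6.2.2, Table KGAA.6.2 or the 6.4 text, and LOCF serves another estimand, hypothetical for every stop.

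Three stronger inferences are tempting, and the documents do not support them.
- A reader might infer that the composite rule is definitely dropped in the four groups and their rates inflated. Table KGAA.6.2 writes the set-to-baseline step with no group limit, and the column layout keeps reading (b) open, under which the error can go the other way.
- A reader might infer that nobody in KGAD+KGAK or KGAB+KGAC enters a primary-estimand estimate. The nested MCMC-MI patients do.
- A reader might infer that the overall summary in 6.1.3 has no method. Section 6.4.1 applies As Observed to all efficacy data.

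**Conclusion.** The conflict between Table KGAA.6.3 footnote b and 6.2.2, Table KGAA.6.2 and the 6.4 text is certain and needs no assumed number. In four groups the result under the primary-estimand label does not in general estimate the 6.2.2 proportion on either reading. Completers-only handling usually overstates it at later visits. Handling that keeps the failures understates it when other dropouts would have responded like completers, and can overstate it when they would have done worse. The SAP does not settle which reading applies, so neither does the direction of the error follow from it. The sizes in the table are illustrations on assumed discontinuation shares and a borrowed response rate, not estimates for these groups. This should be corrected, with modest severity.

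**What to change.** **Full repair.** State that in every analysis group, and in the overall summary of 6.1.3, patients whose recorded reason is lack of efficacy are nonresponders from that point for all binary endpoints in the primary rows of Table KGAA.6.3, and are set to baseline for the continuous ones. Use multiple imputation for other missing data wherever the result is to carry the primary-estimand label. Where it is not run, label the result supportive and show per visit the denominator, the lack-of-efficacy stops and the other dropouts. Extending imputation to all groups is optional; the label must match what is done.

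**Minimum repair.** Limit the primary estimand in 6.2.2, Table KGAA.6.2 and the 6.4 text to the two MCMC-MI groups, remove As Observed from the Primary Estimand rows of Table KGAA.6.3, and label the other groups' results supportive, in line with Table KGAA.6.7.

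**Either way.** State whether terminations under the 5.1.2 rule are coded as lack of efficacy, since 6.2.2 does not say. Reconcile the mention of Addendum 1.1 in the imputation step of 6.4.3 with that section's two-group limit, which excludes those patients.

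**Cost.** The minimum repair is wording only. The full repair adds re-runs on recorded discontinuation reasons, with no new data. Any added analysis should be marked post hoc to the CSR approved on 22 Jan 2025. Rates reported so far on a completers-only basis would usually fall.
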